3.4.6. Prior and Concomitant Therapy

All medications, including over the counter (OTC) drugs and vitamins, taken within 28 days prior to the start of the study will be recorded at Screening. Thereafter, a record of all medications taken during the course of the study will be made. Information regarding the total daily dose, route of administration, start and discontinuation dates, and indication are to be captured on the subject's CRF.

The following prohibitions will apply for the duration of the study:

- There will be no use of systemic/topical anti-inflammatory analgesics which in the opinion of the investigative personnel will interfere with the study results, including anti-inflammatory medications such as aspirin (81 mg aspirin will be allowed at the discretion of the Investigator), Aleve, Motrin, Advil, or Nuprin for 72 hours prior to and during the study (occasional use of acetaminophen will be permitted);
- Use of sunbeds or sunlamps or deliberate exposure of the test sites to natural sunlight or to other sources of ultraviolet (UV) light;
- Participation in any other clinical study;
- Soaking of test areas; and/or
- Application of any product to the test areas.

The use of or change in the dose of any and all concomitant medication, either prescription or OTC, during the study will be recorded. The reason for use or change of dose of a concomitant therapy may need to be reported as an AE. Therapies (medication and non-medication therapies) not restricted by the protocol may be used. Non-prohibited chronic therapies being used at Baseline may be continued.

All topical or systemic medication listed in the exclusion criteria are prohibited during this study. See the IB for information about possible drug-drug interactions.¹

3.4.7. Treatment Compliance

All patches will be applied and removed by investigative personnel. Whereas bathing will be allowed (low tub bath/frontal showers), the patched areas are not to be soaked and are to be kept as dry as possible, per the instructions to be given to each subject. Subjects will be instructed to contact the Investigator before starting any medication, including OTC remedies. In the case of an emergency treatment, the Investigator must be informed as soon as possible. A trained, experienced evaluator will assess study compliance.

Records of patch applications and visit schedule compliance will be recorded on the subjects' CRFs.

If individual patches become dislodged or are misplaced, such that continuous contact with the skin has been interrupted, then patching at that site must be discontinued for the remainder of the study and that patch site will be considered not complete. If all patches become dislodged, the subject will be discontinued from further participation in the study.

3.5. Visit Schedule and Assessments

3.5.1. Study Procedures and Visit Schedule

Screening

At Screening, the subjects will receive any necessary written and verbal information, and the informed consent of each subject will be obtained. Demographic data (including Fitzpatrick skin

type) will be recorded, a medical history will be taken, and previous and concomitant medications will be reviewed. Eligibility will be determined by review of the inclusion/exclusion criteria.

- Any written and verbal information
- Informed consent
- Demographics
- Previous/concomitant medication
- Review of inclusion and exclusion criteria
- Medical history (including lifestyle and habits)
- Examination of application site area

Table 1: Fitzpatrick Skin Types

| | |
|-----|---|
| I | Always burns easily, never tans |
| II | Always burns easily, tans minimally |
| III | Burns moderately, tans gradually |
| IV | Burns minimally, always tans well |
| V | Rarely burns, tans very well |
| VI | Never burn, deeply pigmented ^{4,5} |

Day 1

Prior to randomization, women of childbearing potential will be administered a UPT. If the subject fulfills all of the inclusion and none of the exclusion criteria, he/she will be allowed participation in the study. A Baseline evaluation of the patch sites will be performed prior to application of the patches to ensure that no conditions, markings, or coloration of the skin will interfere with interpretation of the study results. Subjects will receive a unique randomization number, which determines the application scheme of the study materials for that individual subject.

A set of 3 patches will be prepared in accordance with the randomization scheme on either the left or right side of the infrascapular area of the subject's back during the Induction Phase and the opposite side of the infrascapular area of the subject's back during the Challenge Phase. A visual inspection of skin clarity and the side of patch application will be recorded on the CRF to ensure consistent placement of the patches at subsequent visits. A baseline evaluation of the patch sites will be performed immediately prior to application of the patches to ensure that no conditions, markings, or coloration of the skin will interfere with interpretation of the study results. The distance between the patches will be approximately 1 cm. The numbering of the test sites will remain the same throughout the study. A surgical marker will be used to draw lines to indicate the 3 site locations for compliance purposes. All patches will be affixed to the test sites on the intact skin of the infrascapular area of the subject's back by investigative personnel.

CCP-020 (Diacerein 1%) topical ointment and vehicle will be applied in the amount of 0.2 mL to a 2 cm x 2 cm Webril® patch pad via Eppendorf® Combitips and then applied to the subject's skin surface as soon as possible following product application. The sterile 0.9% saline (negative

irritant control) will be applied to a 2 cm x 2 cm Webril® patch pad via pipette and then applied to the subject's skin surface. All 3 products will be evaluated under occlusive patch conditions by means of application to a 2 cm x 2 cm Webril® pad. The patches will be secured with hypoallergenic tape as needed.

Induction

The Induction Phase consists of a series of 9 applications of the study material and subsequent evaluations of the application sites. The subjects will return to the facility 3 times per week for 3 consecutive weeks at 48 – 72 (\pm 4) hour intervals to have the patches removed (i.e. Mondays, Wednesdays, and Fridays for 3 consecutive weeks). Using a tissue, the evaluator will remove any remaining excess study material to avoid transference of materials between sites. The sites will be evaluated using the scoring system detailed in [Section 3.5.5](#). Identical patches will then be applied to the same sites. A new tube of CCP-020 (Diacerein 1%) topical ointment and vehicle will be opened every 14 days due to qualified product suitability (see [Section 3.5.2](#)).

Subjects who are absent once during the 3-week, 9-patch Induction Phase will be instructed to keep the patches in place and return to the facility on their next scheduled visit. They will be scheduled to receive a make-up (MU) patch application at the last Induction visit. The MU patches will be removed 48 – 72 (\pm 4) hours later and the sites will be graded. If subjects fail to return for removal/evaluation of the MU patch, a no ninth grading (N9G) will be recorded.

In cases where the subject misses the 9th evaluation in Induction Phase, the subject will be allowed to remove the patches by themselves in accordance with investigative personnel instructions. A telephone log will be written for any subjects that experience this situation to document the telephone conversation regarding the removal by subject.

Subjects who miss the 9th evaluation, but have had 9 patch applications will be considered to have completed the Induction Phase.

During Induction, the actual patch test grade is a combination of a numerical ([Table 3](#)) and letter ([Table 4](#)) grade consistent with the definitions given in the grading scales. A grade of 3 or higher to a specific study material (see [Section 3.5.5](#) for interpretation of symbols) observed at the first or second reading of the Induction Phase would indicate the subject is pre-sensitized, and application of the product(s) in question would be discontinued. If these reactions are observed after the first or second reading of the Induction Phase, this would necessitate a change in patch location to a naïve site. A second site change to the specific study material would potentially require a patch condition change to semi-occlusive conditions for the remaining applications in the Induction Phase (see [Section 3.5.6](#)).

Rest Period

During the Rest Period of approximately 10-14 days, subjects will not receive any application of study materials.

Challenge

At the Challenge Phase, subjects who have completed the Induction Phase and the Rest Period will have identical patches applied to naïve sites. Patches will remain on the naïve sites for 48 (\pm 1) hour to be evaluated at 30 (+ 10) minutes and 24 (\pm 1), 48 (\pm 1), and 72 (\pm 4) hours following patch removal (e.g., apply patch on Monday, remove patch on Wednesday, evaluate

test sites on Wednesday, Thursday, Friday, and Saturday), using the procedures described above for the Induction Phase. A possible follow-up reading may be conducted at 96 (± 4) hours for subjects with a score of 3 or higher at the 72 (± 4) hour time point.

Concomitant medications and AEs will be reviewed and recorded at the time of evaluation.

To be considered a **completed case**, a subject must have 9 applications of the study material and no fewer than 8 subsequent readings during Induction Phase and one application followed by 4 subsequent readings during the Challenge Phase. Only completed cases will be used to assess sensitization.

Rechallenge

A subject will be rechallenged to a specific study material if, in the opinion of the Investigator, any sign suggestive of contact sensitization (definite erythema with papules and/or edema) is observed at any of the 4 Challenge evaluations or at the Investigator's discretion for that study material.

Rechallenge patches will be applied at least 2 weeks after the end of the Challenge Phase. The study material will be applied to naïve sites on the back, in a manner similar to that used in the Challenge Phase. Rechallenge patches will remain in place for 48 (± 1) hour and patch sites will be evaluated 30 (+ 10) minutes and 24 (± 1), 48 (± 1), and 72 (± 4) hours after removal. As an example, patches will be applied on Monday and removed on Wednesday; the test sites will be evaluated on Wednesday, Thursday, Friday, and the following Saturday.

End of Study

At the EOS, all patches will be removed as described above, and the final evaluations of the test sites will be made.

An EOS examination will be conducted and consist of the following:

- Concomitant medication
- AEs
- UPT in females of childbearing potential

Concomitant medications and AEs will be reviewed and recorded during the whole study. For a detailed listing of scheduled study time points refer to the Visit Schedule and Assessments ([Table 2](#)).

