3.4.5. Assignment to Treatment

3.4.5.1. Randomization

Each subject who signs an informed consent form (ICF) will be assigned a screening number. If the subject meets all of the inclusion and none of the exclusion criteria, and successfully completes the screening procedures, they will be enrolled in the study. Upon enrollment, each subject will be assigned a unique subject number and receive a randomization code, indicating application placement of the study materials. Each subject in this study will serve as his or her own control. All subjects will receive the IPs and control products at adjacent application sites.

The IPs (CCP-020 [Diacerein 1%] topical ointment and vehicle) and study control (saline) will be assigned in a randomized sequence to test Sites 1 through 3 using a set of independent 3-by-3 Latin squares. The same study material will be applied to the same test site throughout the study.

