3.4.5.2. Blinding

The treatments (IPs and control) will not be blinded to investigative personnel involved in the preparation/application and removal of treatments.

Investigative personnel who are involved in the preparation/application and removal of the treatments will not perform the evaluation of skin responses. Investigative personnel who are involved in the preparation/application and removal of the treatments will be unblinded. The trained evaluator who will be evaluating skin responses will be blinded to IPs and control and the treatment allocation; however, because of the demarcations/skin coloration remaining on the skin following patch removal, complete blinding of the evaluators cannot be completely assured.

Investigative personnel, including the Investigator and trained evaluator involved in the evaluation of responses, will remain blinded during the course of the study until Database Lock and finalization of the Statistical Analysis Plan (SAP).

In the event of an emergency, if possible, the Investigator or designee will contact the Sponsor with notification of the intent to unblind the treatment codes prior to the actual unblinding. If it is not possible to notify the Sponsor prior to the unblinding, the Investigator or designee will contact the Sponsor immediately following the unblinding procedure and follow with a written notification to document the exact manner in which the code was broken and the justification for the unblinding. The Investigator will communicate the treatment identification to only the investigative personnel who require the information to manage the emergency. Unblinding will happen on site at TKL.

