3.5.5. Safety Assessments

3.5.5.1. Local Tolerability Assessments

Assessment of the patch sites will be conducted by a trained evaluator once at Baseline (Day 1), 9 times during the Induction Phase, 4 times during the Challenge Phase and, if applicable, 4 times during Rechallenge. The trained evaluator will assign a grade to each site ([Table 3](#)). There will be a main evaluator for the study; a backup evaluator will also be assigned in the event that an emergency occurs and the main evaluator is unable to attend the study visit. For the purpose of statistical analysis only, each grade will correspond to a score. The following symbols and their respective numerical equivalents (see [Table 3](#)) will be used to express the response observed at the time of examination (see [Table 4](#)):

Table 3: Response Symbols and Numerical Equivalents

| Grade | Score* | Definition |
|--------------|---------------|---|
| 0 | 0 | No evidence of irritation |
| 1 | 1 | Minimal erythema; barely perceptible |
| 2 | 2 | Definite erythema, readily visible; or minimal edema; or minimal papular response |
| 3 | 3 | Erythema and papules |
| 4 | 3 | Definite edema |
| 5 | 3 | Erythema, edema, and papules |
| 6 | 3 | Vesicular eruption |
| 7 | 3 | Strong reaction spreading beyond test site |

*Scores are utilized only during the statistical analysis process of the study. Grades will be conducted throughout the study by the trained evaluator.

Table 4: Effects on Superficial Layers of Skin

| Grade | Score* | Response |
|-------|--------|--|
| A | 0 | Slight glazed appearance |
| C | 1 | Marked glazing |
| E | 2 | Glazing with peeling and cracking |
| F | 3 | Glazing with fissures |
| G | 3 | Film of dried serous exudate covering all or portion of the patch site |
| H | 3 | Small petechial erosions and/or scabs |

*Scores are utilized only during the statistical analysis process of the study. Grades will be conducted throughout the study by the trained evaluator.

Other notations (see [Table 5](#)) may be made in place of a score to designate particular circumstances preventing the assignment of a score or in addition to a score to identify damage to the epidermis and/or spreading of a reaction beyond the patch site.

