4.6. Safety Evaluation

4.6.1. Cumulative Irritancy

Cumulative irritancy during Induction will be quantified by means of the cumulative irritancy index (CII), defined as the mean of the total cumulative irritation scores received during the Induction Phase (9 readings). The total cumulative irritation score for each subject and product will be calculated by summing each individual's scores on each of the 9 evaluation days in the Induction Phase. Response grades will be assigned numerical scores according to [Table 3](#) and [Table 4](#). Once the maximum score (combined score from [Table 3](#) and [Table 4](#)) or a 3 or greater is achieved, the remaining scores of 3 will be carried forward through all subsequent readings. No data imputations are to be made for discontinued subjects or missed evaluations.

The CII will be tested pairwise for product differences using Fisher's protected least significant differences in the context of the 2-way analysis of variance (ANOVA) including main effects of subject and product, without interaction. Pairwise differences will be tested for all products at the 5% level. Mean cumulative irritation scores will also be presented for each patch in a listing.

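### The blinded evaluator is told to wipe study material off the sites just before grading, which conflicts with the blinding section and can plausibly reveal the saline site.

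*Combined protocol and SAP*

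**What the plan says.** Section 3.4.5.2 (Blinding) sets a rule on roles: "Investigative personnel who are involved in the preparation/application and removal of the treatments will not perform the evaluation of skin responses". It adds: "Investigative personnel who are involved in the preparation/application and removal of the treatments will be unblinded". The trained evaluator is to be blinded to the products and their allocation. The section concedes that this cannot be guaranteed, and the only reason it gives is marks or discoloration left on the skin once the patch is off.

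Section 3.5.5.1 identifies the grader: "The trained evaluator will assign a grade to each site". One main evaluator is planned, with a backup.

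Section 3.5.1, under Induction, describes each visit. The patches come off, and then: "Using a tissue, the evaluator will remove any remaining excess study material to avoid transference of materials between sites". The sentence after that starts the grading: "The sites will be evaluated using the scoring system detailed in" section 3.5.5. New patches follow.

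Three further statements bear on the point:

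- Section 3.4.5.1: "The same study material will be applied to the same test site throughout the study".
- Section 3.5.1, on the Challenge readings: "using the procedures described above for the Induction Phase".
- Section 4.6.1, on cumulative irritancy: "Pairwise differences will be tested for all products at the 5% level".

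**The concern.** The person who must not know the allocation is given a task that involves handling the products. If removing the treatments includes removing what is left of them on the skin, sections 3.4.5.2 and 3.5.1 contradict each other. If it means only lifting the patch, there is no formal contradiction, but the separation of roles loses its purpose, because the grader handles the material moments before scoring.

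The contrast between the products makes unmasking plausible for saline. Two materials are ointments; exclusion criterion 7 lists mineral oil, petrolatum and D&C Yellow #10 among the constituents of the materials evaluated. The third is a saline solution. Nothing in the documents shows that wiping would separate CCP-020 from its vehicle, and that is not claimed here.

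At stake are the visual Induction grades. The low end of the scale is a matter of judgement: grade 1 in Table 3 is erythema that can barely be seen. Two of the three pairwise irritancy comparisons involve saline, and these comparisons are the only hypothesis tests that section 4 specifies. Using each subject as his or her own control does not help if the grader knows which of the adjacent sites is saline.

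**Working it through.** **Step 1. Who does what**

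| Task | Role under 3.4.5.2 | Role under 3.5.1 and 3.5.5.1 |
|---|---|---|
| Removal of treatments | Unblinded staff who do not grade | Patches: role not named in the Induction text; residue: the evaluator |
| Grading | Blinded trained evaluator | The trained evaluator, right after wiping |

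The roles meet at the residue step. The caveat in 3.4.5.2 concerns the look of the skin after patch removal, so it does not cover this step.

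**Step 2. Readings affected**

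- Induction: up to 9 of 9 readings per subject directly follow wiping.
- Challenge: at most 1 of 4 readings, the one 30 minutes after patch removal, and only if the cross-reference to the Induction procedures includes wiping. The same applies to Rechallenge, which is run in a similar manner.

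**Step 3. The plan's own figure**

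Section 4.2 gives a 95% upper bound of 1.5% for no reactions in 200 subjects. The exact one-sided bound is 1 − 0.05^(1/200) = 1.487%, and 3/200 = 1.5%. The figure reproduces and does not depend on this point.

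**Step 4. How small a grading shift would matter**

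This is a sensitivity threshold, not an estimate of bias. The inputs are 200 subjects (4.2), three products, a two-way ANOVA on subject and product, Fisher's protected LSD and the 5% level (4.6.1). Assume no true difference between products and the same upward shift *b* at both ointment sites. Let SD be the standard deviation of the paired difference in the nine-reading total, taken as equal for all pairs.

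- Error df = 199 × 2 = 398; F(0.05; 2, 398) = 3.018; t = 1.966.
- Product means *b*, *b*, 0 have grand mean 2*b*/3. Product sum of squares = 200 × (2 × (*b*/3)² + (2*b*/3)²) = 400*b*²/3. Mean square on 2 df = 200*b*²/3.
- Error mean square = SD²/2.
- F = (200*b*²/3) / (SD²/2) = 400*b*² / (3 SD²).
- Setting F = 3.018: *b* = SD × √(3 × 3.018/400) = 0.150 SD.
- The pairwise LSD is 1.966 × SD/√200 = 0.139 SD. It is smaller, so the overall F test is the binding limit.

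The documents give no SD. Over an assumed range:

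| Assumed SD (points, nine-reading total) | Threshold *b* (points) | Per reading (*b*/9) |
|---|---|---|
| 2 | 0.30 | 0.033 |
| 4 | 0.60 | 0.067 |
| 6 | 0.90 | 0.100 |

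The last column corresponds to one extra point at about 3%, 7% and 10% of ointment-site readings.

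Two qualifications apply. First, 0.150 SD is the threshold for the *observed* shift; if it were the *expected* shift, the overall test would be significant in about 58% of trials (noncentral F, 2 and 398 df). Second, 4.6.1 carries a score of 3 forward to all later readings. One altered call from 2 to 3 can therefore add more than one point to the total, and a site already at 3 has no later score left to alter. The conversion to a percentage of readings is approximate.

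**The case against.** The best defence is that removal in 3.4.5.2 means taking off patches. Section 3.4.7 uses the word that way, and wiping can be seen as a separate step to prepare the site. That reading is arguable, although 3.4.5.2 itself explains the treatments as the products and control rather than the patches. It would remove the formal contradiction but not the exposure of the grader to the material.

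A second argument is that blinding is already admitted to be imperfect and that ointment sites may look different from saline whoever wipes them. This stands in part. The documents do not describe the residue after 48 to 72 hours under a patch, so the gain from moving the task cannot be measured. But skin coloration is largely inherent in the products, whereas the evaluator's handling of residue is created by the procedure and can be avoided.

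Third, irritancy is not the primary objective. Section 2 names sensitization, and section 3.2 says that detecting irritation is not the main purpose of the method. This limits the consequence and is accepted. The irritancy comparisons are still formal tests that will be reported, and section 3.1 also uses Induction reactivity patterns in interpreting sensitization.

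Fourth, the Challenge cross-reference may concern grading only, and the aim given for wiping, avoiding transfer between sites, appears only under Induction. That is fair, so the Challenge effect is stated as conditional.

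Finally, the threshold rests on an assumed SD, no true difference and an equal shift at both ointment sites. It shows that 200 subjects make the test sensitive to small shifts from any cause; it does not show that such a shift will occur.

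**Conclusion.** The concern holds. Followed as written, 3.5.1 has the blinded grader handle study material immediately before grading, against the separation of roles in 3.4.5.2, or at least against its purpose. The conflict is certain as a matter of wording. That it would reveal the saline site is plausible but not demonstrated, and its effect on the grades cannot be estimated from the documents.

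The exposure covers all scheduled Induction readings, and so the two irritancy comparisons with saline. There, an observed shift of well under one point to just under one point on the nine-reading total would be enough for significance under the stated assumptions. The comparison of CCP-020 with vehicle is not shown to be affected. The sensitization call is less exposed because it is made in absolute terms on Challenge and Rechallenge grades. The sample size does not change. The point should be corrected because the source of bias is avoidable at almost no cost.

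**What to change.** - In 3.5.1, assign the wiping to the unblinded staff who remove the patches. State that it is done in the same manner at all three sites, saline included, and is finished before the evaluator sees the back.
- Apply the same rule wherever patches come off before a reading: Induction, Challenge and Rechallenge.
- In 3.4.5.2, state that removal of the treatments includes removal of residue from the skin.

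The cost is a wording change in two sections. Unblinded staff are already assigned to removal, so no additional people or visits are needed, and the protection against transfer between sites is kept. The limit that 3.4.5.2 already discloses, marks or coloration on the skin, remains.

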3.3. Study Population

3.3.1. Subject Population

A sufficient number of subjects will be enrolled in order to provide 200 completed subjects evaluable for analysis; an individual subject will be allowed to participate in the study one time only.

A rationale for the choice of sample size is provided in [Section 4.2](#) of this protocol.

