3.6.6. Expected Adverse Events

Any observed response in the patch test area that can be denoted using the irritation criteria summarized in [Table 3](#) and [Table 4](#) will not be considered an AE.

Tape related reactions will only be recorded as AEs when the subject is discontinued due to tape reaction around all sites. When 1 or 2 sites are experiencing severe tape related reactions, the application site will be stopped and the subject will continue on the study. This will be noted in the database as "T" as indicated in [Table 5](#) and will be considered an expected AE. When all application sites are experiencing tape reaction, the subject is discontinued and therefore be recorded as an AE. The subject will be followed up through resolution.

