4. STATISTICAL METHODS

4.1. General Considerations for Data Analysis

The RIPT study design using 200 subjects is considered adequate to identify any significant safety hazard due to the potential of a topically administered dermatologic agent to induce allergic sensitization. Individual subjects' cutaneous responses after Challenge Phase are classified as indicative of sensitization or not indicative of sensitization based on specific criteria defined in terms of an ordinal rating scale. The occurrence in this study of even a single reaction indicative of sensitization is sufficient to suggest that the test product may have the potential to cause hypersensitivity.

The statistical analyses described below will be supplemented by a comprehensive Statistical Analysis Plan (SAP) which will be finalized before the database is locked. Any changes to the statistical plans will be described and justified in the final report.

All statistical processing will be performed using the SAS® system (version 9.2 or higher). No interim or subgroup analyses are planned.

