4.3. Subject Populations for Analysis

All subjects who receive treatment will be evaluable for AEs. The evaluation of sensitization will be based on all subjects who complete the Challenge Phase of the study. The analysis of cumulative irritancy will be based on all subjects who complete the Induction Phase of the study.

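### Sections 3.5.1 and 4.3 define the sensitization set differently, and the completed-case rule, read literally, can leave out subjects because they reacted or missed one Challenge reading

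*Combined protocol and SAP*

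**What the plan says.** Section 3.5.1 (Challenge) defines a completed case by nine Induction applications, at least eight Induction readings, one Challenge application and four Challenge readings, and adds: "Only completed cases will be used to assess sensitization".

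Section 4.3 defines the set differently: "The evaluation of sensitization will be based on all subjects who complete the Challenge Phase of the study". It sets no minimum for Induction and does not say whether completion is judged by subject or by product.

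Section 3.3.1 fixes the target: "A sufficient number of subjects will be enrolled in order to provide 200 completed subjects evaluable for analysis".

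Four places deal with a reaction during Induction after the second reading:

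- Section 3.5.1 (Induction) moves the patch: "If these reactions are observed after the first or second reading of the Induction Phase, this would necessitate a change in patch location".
- Section 3.5.6 also moves it, at most twice per product, and then ends that product for the rest of the study. Subjects who were moved stay evaluable for sensitization if they receive at least nine applications.
- Section 3.3.3 ends further applications of the product after a grade of 3 or greater, having said that patches *may* be discontinued. Its next paragraph changes the site after a reaction.
- Section 3.5.5.1 discontinues the patch site. It writes the threshold as above 3, yet its worked example stops at exactly 3.

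Section 4.6.2 takes the sensitization call from Challenge, confirmed if necessary at Rechallenge. Section 4.1 sets the decision rule: "The occurrence in this study of even a single reaction indicative of sensitization is sufficient to suggest" that the product may cause hypersensitivity.

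**The concern.** The study's conclusion can turn on one subject, so the rule for who is assessed matters more than it would for a mean or a rate. Two kinds of reacting subject can fall outside the Section 3.5.1 set: one who reacts at Challenge but misses another Challenge reading, and one whose CCP-020 is stopped for Induction reactions before any CCP-020 Challenge. In both, inclusion depends partly on the reaction or on a missed visit, and the subjects lost are reactors. Any resulting bias therefore favours a finding of no sensitization.

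The plan has a scoring rule for stopped sites in the irritancy analysis ("the remaining scores of 3 will be carried forward through all subsequent readings", Section 4.6.1). The supplied text has no matching rule for sensitization, although Section 3.1 makes the Induction reaction pattern part of the interpretation. Adverse event tables will not show these reactions either, because Section 3.6.1 excludes responses that can be graded on Tables 3 and 4.

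**Working it through.** **1. The plan's own figure.** Inputs: 0 reactions in 200 evaluable subjects (Section 4.2). Exact one-sided 95% upper bound: 1 − 0.05^(1/200) = 1.487%. The rule of three gives 3/200 = 1.5%. The stated 1.5% is reproduced as a one-sided bound (a two-sided 95% interval would end at 1.83%).

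**2. When CCP-020 can be stopped after reading 2.** In Section 3.5.1 the next patch goes on at the visit of the current reading, so a stop at reading *r* leaves *r* applications.

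- Sections 3.5.1 and 3.5.6: two moves, then a stop. This needs three qualifying reactions within readings 3 to 9, so the third falls at readings 5 to 9, after 5 to 9 applications.
- The termination sentence in Section 3.3.3, taken alone: one reaction at readings 3 to 9 could be enough, after 3 to 9 applications. The site-change paragraph that follows points the other way.
- A stop before reading 9 leaves fewer than nine applications. A stop at reading 9 leaves nine, but ending the product for the rest of the study removes the Challenge patch.

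**3. The two definitions applied to each kind of subject.**

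| Subject | Section 3.5.1 | Section 4.3 | Call under Section 4.6.2 |
|---|---|---|---|
| Table 3 grade of 3 or more at one Challenge reading, another reading missed | Out: fewer than four readings | Unclear: completing Challenge is not defined | Still possible through Rechallenge; described in the narrative |
| CCP-020 stopped before reading 9 | Out: too few applications, no CCP-020 Challenge | May be in, through vehicle and saline | Not possible |
| CCP-020 stopped at reading 9 | Out: no CCP-020 Challenge, although Section 3.5.6 calls nine applications evaluable | May be in, as above | Not possible |
| Site moved, nine applications, full Challenge | In | In | Possible |

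That a subject can continue on other products after one is stopped follows from the product-level wording of Sections 3.3.3 and 3.5.6. Section 3.4.7 ("patching at that site must be discontinued for the remainder of the study and that patch site will be considered not complete") and Section 3.6.6 ("the application site will be stopped and the subject will continue on the study") work at site level too, but they concern dislodged patches and tape reactions, so they support the reading only indirectly.

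**4. Illustrative bounds.** The documents give no stopping rate, so the number stopped, *s*, is assumed. Bounds are exact one-sided 95% (Clopper-Pearson): the 0.95 quantile of Beta(x+1, n−x) for x events in n. The worst case treats every unchallenged stopped subject as an event.

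| s (assumed) | Section 3.5.1 set, worst case s/(200+s) | Section 4.3 set, no events 0/(200−s) | Section 4.3 set, worst case s/200 |
|---|---|---|---|
| 1 | 1/201: 2.34% | 0/199: 1.49% | 1/200: 2.35% |
| 2 | 2/202: 3.08% | 0/198: 1.50% | 2/200: 3.11% |
| 5 | 5/205: 5.06% | 0/195: 1.52% | 5/200: 5.18% |

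Under Section 3.5.1, with enrolment continuing to 200 completed subjects, the figure stays at 0/200 and 1.49% whatever *s* is. That stopped subjects are replaced is inferred from Section 3.3.1; there is no explicit replacement rule. The middle column shows that correcting the denominator alone hardly matters. What matters is how unchallenged reactors are treated.

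**The case against.** The strongest reply is that little is lost. Sections 3.5.1 and 3.5.6 move the patch, and three qualifying reactions are needed before CCP-020 stops, so few subjects may be affected. A stopped subject has no CCP-020 Challenge and cannot meet the Section 4.6.2 criterion in whichever set that subject is placed; the loss comes from the stopping text more than from the completed-case sentence. Some stops will be irritant, since Table 4 scores are additive (2C = 3). A Challenge reactor with a missed reading can still be rechallenged and is described in the narrative, and the single-reaction rule is not expressly limited to completed cases. Because only subjects who completed Induction enter Challenge, Section 4.3 can be read as shorthand for Section 3.5.1. Section 4.6.2 plans no confidence bound, and Section 4.1 promises an SAP that may settle all of this.

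Most of that limits the size of the problem and is accepted. It does not remove the problem. Section 3.5.1 states a restriction that, as written, excludes a Challenge reactor with one missing reading. Section 4.3 does not repeat that restriction, and no text says whether completion is judged by product. The narrative in Section 4.6.2 covers Challenge and Rechallenge reactions only, so a subject stopped in Induction falls outside it.

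A reader might infer that a single Induction reaction removes a subject, so that many reactors disappear. The documents do not support that: the termination sentence in Section 3.3.3 is followed by a site-change paragraph and contradicted by Section 3.5.6.

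**Conclusion.** The two definitions conflict. Read literally, the completed-case rule lets inclusion depend on the reaction (stopped subjects) or on a missed reading (partial Challenge). Under the single-reaction rule any bias is towards no sensitization. Its size is unknown, and it is nil if nobody is stopped or all stops are irritant and no Challenge reactor misses a reading.

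Two stronger conclusions are tempting and should not be drawn. First, the 1.5% is not wrong: it is the correct bound for 0/200 and describes subjects with a completed CCP-020 case. The worst-case figures of 2.34% to 5.18% rest on assumed counts of 1, 2 or 5 with every stop treated as an event; they do not estimate the true rate. Second, the plan does not discard confirmed positives. An unchallenged Induction reactor does not meet the plan's criterion, and a partial-Challenge reactor still has a route through Rechallenge and the narrative.

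Subjects stopped at the first or second reading are labelled pre-sensitized and form a separate group. The correction is worth making before database lock because it is cheap and the possible error runs one way.

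**What to change.** 1. Use one by-product definition in Sections 3.5.1 and 4.3. Classifying a subject as not sensitized to a product requires a completed case for that product. Any Table 3 grade of 3 or more at any Challenge reading is included and assessed under Section 4.6.2, even if other readings are missing.
2. List and describe, by product, every subject stopped for Induction reactions, showing separately those stopped at reading 1 or 2. Do not count unchallenged subjects as non-events in the CCP-020 denominator.
3. If a confidence bound is reported, state that it applies to completed CCP-020 cases and add a worst-case sensitivity bound that counts unchallenged subjects stopped after reading 2 with a Table 3 grade of 3 or more as possible events. Relabelling the planning figure in Section 4.2 is optional.
4. Reconcile Sections 3.3.3, 3.5.1, 3.5.5.1 and 3.5.6 on when patching stops and when the site is moved, because they decide who is analysed. No clinical rule is proposed here.

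The cost is wording in the protocol and SAP, one listing, one extra line if a bound is reported, and possibly a less favourable reported bound. No additional subjects or visits are needed.
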